5.3. Screening/Baseline/Run-in Failures

Screen failures are defined as subjects who consent to participate in the clinical trial but are never subsequently randomized. In order to ensure transparent reporting of screen failure subjects, meet the Consolidated Standards of Reporting Trials (CONSORT) publishing requirements, and respond to queries from Regulatory authorities, a minimal set of screen failure information is required including Demography, Screen Failure details, Eligibility Criteria, and Serious Adverse Events (see Section [7.4.1.5](#)).

5.3.1. Re-Screening

If a subject has not met all the eligibility criteria within the 28 day screening period, re-screening is required. Subjects are only allowed to be re-screened once; the entire screening process must be repeated.

If a blood sample has to be withdrawn due to sample handling problems, breakage or sample integrity, this is not considered a re-screening.

Further details regarding the procedure for re-screening may be found in the Study Reference Manual (SRM).

5.3.2. Re-Testing – Laboratory Exclusion

If a subject fails any of the laboratory exclusion criteria, the test may be repeated twice within the screening period. If the subject fails the laboratory criteria for a third time they will be considered a screen failure; these subjects may be re-screened as described in Section [5.3.1](#).

If a blood sample has to be withdrawn due to sample handling problems, breakage or sample integrity, this is not considered a re-testing.

Further details regarding the procedure for re-testing may be found in the SRM.

5.4. Withdrawal/Stopping Criteria

The following actions must be taken in relation to a subject who fails to attend the clinic for a required study visit:

- The site must attempt to contact the subject and re-schedule the missed visit as soon as possible.
- The site must counsel the subject on the importance of maintaining the assigned visit schedule and ascertain whether or not the subject wishes to and/or should continue in the study.
- In cases where the subject is deemed ‘lost to follow up’, the investigator or designee must make every effort to regain contact with the subject (where possible, 3 telephone calls and if necessary a certified letter to the subject’s last known mailing address or local equivalent methods). These contact attempts should be documented in the subject’s medical record.

- Should the subject continue to be unreachable, only then will he/she be considered to have withdrawn from the study with a primary reason of “Lost to Follow-up”.

A subject may withdraw from study treatment at any time at his/her own request, or may be withdrawn at any time at the discretion of the investigator for safety, behavioural or administrative reasons.

In addition, study medications will be discontinued and the subject withdrawn from the study in the event of any of the following:

- All serious infections.
- Pregnancy.
- Confirmed PAP
- Severe or serious hypersensitivity reactions, including anaphylaxis.
- If the liver chemistry stopping criteria (Section 5.4.1) or QTc stopping criteria (Section 5.4.2) are met.
- Other serious or severe adverse events, at the discretion of the Investigator, after consultation with the GSK Medical Monitor.
- Persistent or recurrent hematologic laboratory abnormalities (see Section 5.5.2).

If a subject withdraws from the study, he/she may request destruction of any samples taken, and the investigator must document this in the site study records. In each case the reason for withdrawal will be recorded in the eCRF.

A subject that is withdrawn early from the study after being randomized to treatment cannot be re-screened, but should be encouraged to return for the Early Withdrawal visit.

[figure not shown]

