5.4.2. QTc Stopping Criteria

- The *same* QT correction formula *must* be used for *each individual subject* to determine eligibility for and discontinuation from the study. This formula may not be changed or substituted once the subject has been enrolled.
- For example, if a subject is eligible for the protocol based on QTcB, then QTcB must be used for discontinuation of this individual subject as well.
- Once the QT correction formula has been chosen for a subject's eligibility, the *same formula* must continue to be used for that subject *for all QTc data being collected for data analysis*. Safety Electrocardiogram (ECGs) and other non-protocol specified ECGs are an exception.
- The QTc should be based on averaged QTc values of triplicate electrocardiograms obtained over a brief (e.g. 5-10 minute) recording period.

A subject who meets either of the bulleted criteria below will be withdrawn from the study:

- QTc > 500 msec OR Uncorrected QT > 600 msec
- Change from baseline of QTc > 60 msec

For patients with underlying **bundle branch block**, follow the discontinuation criteria listed below:

| Baseline QTc with Bundle Branch Block | Discontinuation QTc with Bundle Branch Block |
|---------------------------------------|--|
| < 450 msec | > 500 msec |
| 450 – 480 msec | ≥ 530 msec |

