5.5. Treatment withdrawal

Subjects will be permanently withdrawn from study treatment if any of the following respiratory symptoms or hematologic abnormalities are seen, investigation will be carried out as described below. After withdrawal of treatment under these conditions, where possible subjects should remain in the study (off treatment) in order to complete all remaining visits/assessments.

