6.4. Blinding

The study will be double-blind (sponsor unblind), which means that the subject, investigator and trial staff at site (apart from unblinded administrator(s) and pharmacy staff), will be blinded to the trial treatment allocated to each individual subject. In addition, the sponsor central and local study teams will be blinded to treatment allocations, except for roles required to be ‘unblind’ in order to manage study conduct and oversight (including unblinded monitor(s)) and roles specified in the Reporting and Analysis Plan (RAP) as involved with the preparation and review of the planned interim analyses.

The RAP, which will be approved prior to the first unblinding, will identify the specific GSK individuals involved; outline in detail the activities of the interim analyses, and how the integrity of the study will be maintained.

At sites, there will be at least one unblinded administrator (study co-ordinator or nurse) who will prepare and administer the study treatment.

In the case of emergency unblinding (eg. through RAMOS NG or GSK Clinical support help desk), the following will apply:

- The investigator or treating physician may unblind a subject’s treatment assignment **only in the case of an emergency** OR in the event of a serious medical condition when knowledge of the study treatment is essential for the appropriate clinical management or welfare of the subject as judged by the investigator.
- Investigators have direct access to the subject’s individual study treatment.
- It is preferred (but not required) that the investigator first contacts the Medical Monitor or appropriate GSK study personnel to discuss options **before** unblinding the subject’s treatment assignment.
- If GSK personnel are not contacted before the unblinding, the investigator must notify GSK as soon as possible after unblinding, but without revealing the treatment assignment of the unblinded subject, unless that information is important for the safety of subjects currently in the study.
- The date and reason for the unblinding must be fully documented in the eCRF

A subject will be withdrawn if the subject’s treatment code is unblinded by the investigator or treating physician. The primary reason for discontinuation (the event or condition which led to the unblinding) will be recorded in the eCRF.

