7.1.3. Follow-up visit and early withdrawal* procedures list

*for early withdrawal, follow Day 85 procedures, then schedule a follow up visit.

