9.3. Data Analysis Considerations

9.3.1. Analysis Populations

Intent to Treat (ITT) population: The ITT population is defined as all subjects who were randomised to treatment and who received at least one dose of study treatment. This population will be based on the randomised treatment group.

Safety population: The safety population is defined as all subjects who receive at least one dose of study treatment. This population will be based on the actual treatment received.

Pharmacokinetic (PK) population: The PK population is defined as all subjects who are in the 'Safety' population and who have at least one valid PK assessment.

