| 
treatment and may continue subject in the study for any protocol specified follow up assessments
 
MONITORING:
 
For bilirubin or INR criteria:
 
 Repeat liver chemistries (include ALT, AST, alkaline phosphatase, bilirubin) and perform liver event follow up assessments within 24 hrs Monitor subjects twice weekly until liver chemistries resolve, stabilize or return to within baseline A specialist or hepatology consultation is recommended 
For All other criteria:
 
 Repeat liver chemistries (include ALT, AST, alkaline phosphatase, bilirubin) and perform liver event follow up assessments within 24-72 hrs Monitor subjects weekly until liver chemistries resolve, stabilize or return to within baseline | 
form including acetaminophen, herbal remedies, other over the counter medications.
 
 Record alcohol use on the liver event alcohol intake case report form 
For bilirubin or INR criteria:
 
 Anti-nuclear antibody, anti-smooth muscle antibody, Type 1 anti-liver kidney microsomal antibodies, and quantitative total immunoglobulin G (IgG or gamma globulins). Serum acetaminophen adduct HPLC assay (quantifies potential acetaminophen contribution to liver injury in subjects with definite or likely acetaminophen use in the preceding week [James, 2009]). NOTE: not required in China Liver imaging (ultrasound, magnetic resonance, or computerised tomography) and /or liver biopsy to evaluate liver disease: complete Liver Imaging and/or Liver Biopsy CRF forms. |

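### A subject withdrawn from the study for a listed safety event before Day 43 has no Week 6 pain score, although the score comes from a home diary, and the retention rules conflict for liver and hematologic stops

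*Protocol*

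**What the plan says.** Section 5.4 joins two acts, stopping the drug and leaving the study: "In addition, study medications will be discontinued and the subject withdrawn from the study in the event of any of the following". The list covers serious infections, pregnancy, confirmed PAP, severe or serious hypersensitivity, the liver and QTc criteria, other serious or severe adverse events at the investigator's discretion, and persistent or recurrent hematologic abnormalities. Section 5.4.2 repeats it for QTc: "A subject who meets either of the bulleted criteria below will be withdrawn from the study". The risk table in 4.7.1 repeats it for serious infection, hypersensitivity and pregnancy. Section 6.4 also withdraws a subject whose "treatment code is unblinded by the investigator or treating physician", without saying whether this means from treatment or from the study.

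After withdrawal, the subject "should be encouraged to return for the Early Withdrawal visit". Section 7.1.3 describes that visit: "for early withdrawal, follow Day 85 procedures, then schedule a follow up visit".

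Two places take a different line on retention. For respiratory and hematologic stops, Section 5.5 says "where possible subjects should remain in the study (off treatment) in order to complete all remaining visits/assessments". For liver stops, Appendix 2 (12.2) tells the site, where restart is not allowed, to permanently discontinue study "treatment and may continue subject in the study for any protocol specified follow up assessments".

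The primary endpoint is the Week 6 change from baseline in a 7-day mean of a daily pain NRS that subjects complete at home (Sections 3 and 7.3.1). The ITT population is "all subjects who were randomised to treatment and who received at least one dose of study treatment" (9.3.1).

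**The concern.** The primary score needs no drug and no clinic visit, only a questionnaire of 1-2 minutes a day (Section 7). A subject who leaves the study at Week 3 under 5.4 still counts in the ITT population but has no Week 6 value. The value is missing because of a participation rule, not because it could not be recorded.

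The MMRM then has to treat the value as missing at random. The missingness follows from safety events after randomisation, and 4.7.1 lists infection and hypersensitivity as potential risks of the drug, so the losses may differ by arm. Section 9.4.1 promises sensitivity analyses for missing data. These can vary the assumption, but they cannot recover scores that were never recorded. Whether data are collected after treatment stops is decided in the protocol, so a later analysis plan cannot repair it.

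**Working it through.** **1. Who loses the score.** Week 6 is Day 43, so the 7-day mean uses roughly Days 36 to 42. Five of the eight doses (Days 1, 8, 15, 22, 29) fall before that window. A subject withdrawn at or after the Week 6 visit already has the primary score. A subject withdrawn before it has none, or only a partial week.

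**2. The retention rules side by side.**

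| Reason for stopping | Stay in the study? | Where |
|---|---|---|
| Serious infection, severe or serious hypersensitivity | No | 5.4, 4.7.1 |
| QTc criteria | No | 5.4, 5.4.2 |
| Unblinding by investigator or treating physician | Withdrawn, object not stated | 6.4 |
| Persistent respiratory symptoms or DLCO fall | Yes, where possible | 5.5, 5.5.1 |
| Hematologic abnormalities | No in 5.4; yes, where possible, in 5.5 | 5.4, 5.5, 5.5.2 |
| Liver criteria | No in 5.4; may continue in Appendix 2 | 5.4, 12.2 |

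The last two rows contradict each other within the document. One could try to read 5.4 as a later step for hematologic values that persist or recur. However, 5.4 refers to 5.5.2 for these, and 5.5.2 defines no such step.

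**3. The plan's own power figure.** Inputs from 9.1 and 9.2.1: 20 per arm, difference 2.7, SD 3, two-sided 5%, t-test.

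- Standard error = 3 × √(2/20) = 0.949.
- Minimal significant difference = t(0.975; 38 df) × 0.949 = 1.92, stated as approximately 2.
- Power by noncentral t = 79.2%, stated as approximately 80%.

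The stated figures reproduce. The 20 per arm in the calculation equals the 20 per arm to be randomised (4.4), so no allowance is made for missing Week 6 scores.

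**4. Power with lost scores.** The documents give no rate of stopping before Week 6, so I assume 0 to 20% and use the same t-test on the scores that remain.

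| Lost per arm | Power, both arms lose | Minimal significant difference | Power, active arm only loses |
|---|---|---|---|
| 0 | 79.2% | 1.92 | 79.2% |
| 1 (5%) | 77.0% | 1.97 | 78.1% |
| 2 (10%) | 74.6% | 2.03 | 76.9% |
| 3 (15%) | 72.1% | 2.10 | 75.6% |
| 4 (20%) | 69.3% | 2.17 | 74.1% |

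**5. Bias in a one-sided worst case.** Suppose that k active subjects and no placebo subjects are lost, and that each one's unseen change is 2.7 points worse than the model predicts. The treatment difference is then overstated by (k/20) × 2.7:

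- k = 1: 0.05 × 2.7 = 0.135, about 0.14 points.
- k = 2: 0.10 × 2.7 = 0.27 points.
- k = 4: 0.20 × 2.7 = 0.54 points, which would need a fifth of the arm to be stopped within six weeks.

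The objective in 4.5 is 2 points.

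**The case against.** The strongest reply is that few subjects will be affected. In the earlier RA study described in 2.2.4, infections occurred in 26.1% of active and 29.6% of placebo subjects. Hospitalisation made events serious in one of 69 active and one of 27 placebo subjects. Section 4.7.1 reports no allergic or acute systemic reactions to date, though it does report one septic shock in a healthy volunteer. At 1/69, the expected loss in 20 subjects is 20/69 = 0.29. By the formula above the bias is 0.29/20 × 2.7 = 0.04 points. That study used IV dosing in RA, so the figure is only indicative. The reply stands as a limit on size. A reader might infer that these losses are likely to be related to arm, but the documents support only that they may be.

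Two other inferences go too far. One is that the primary score is lost for every subject withdrawn under 5.4; this is true only of stops before Day 43. The other is that 6.4 expressly ends study participation. That is its natural reading, but the text says only that the subject is withdrawn. Nor do the responder endpoints add to the overstatement in step 5. Missing scores count as non-response (9.4.2), which works against whichever arm loses more subjects.

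It can also be said that a subject in hospital, or taking analgesics prohibited by 6.10.2, gives pain scores that do not reflect the drug. Whether to use such scores is a choice of estimand. Collecting them does not force their use, whereas not collecting them removes the choice.

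Finally, the procedures list in 7.1.3 and the notes to the schedule in 7.1.2 are not legible in the text at hand. In the readable text, only 7.2 carries the diary to Week 12, and it addresses subjects taking part in the study. Nothing readable continues it for those withdrawn.

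**Conclusion.** The point holds in a limited form. For the 5.4 events, and on the natural reading for unblinding under 6.4, a stop before Day 43 leaves an ITT subject without a Week 6 score that a home diary could usually have supplied. The likely size is small. One score lost per arm costs about two points of power (79.2% to 77.0%), and four per arm cost about ten (to 69.3%). The bias figures of 0.14 and 0.27 points rest on losses in the active arm only and on a 2.7-point shortfall in each lost subject, so they are upper illustrations and not forecasts. All of these figures depend on an assumed stopping rate, because the documents give none.

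Separately, and whatever the rate, 5.4 contradicts 5.5 and 5.5.2 on hematologic stops and Appendix 2 on liver stops. Sites cannot tell from the text whether such subjects stay in the study, and the passages must be reconciled. The change is worth making because it is cheap and reduces reliance on an untestable assumption in an arm of 20.

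**What to change.** Leave every treatment-stopping rule as it is. In 5.4, 5.4.2, 6.4, 7.1.3 and the matching rows of 4.7.1, separate stopping treatment from stopping data collection:

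- Unless consent is withdrawn, the daily pain NRS and paracetamol diary continues where possible at least through Day 43, and preferably to Week 12.
- Any use of prohibited analgesics in that period is recorded, so that the analysis can decide how to handle those scores.
- The exit visit with Day 85 procedures is kept as an additional safety visit.
- Section 6.4 states whether withdrawal after unblinding is from treatment or from the study.
- Sections 5.4, 5.5, 5.5.2 and Appendix 2 are reconciled on whether hematologic and liver cases remain in the study.

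The cost is amendment wording and a few weeks of a 1-2 minute diary in a handful of subjects. The downside is that small burden on people who have already stopped treatment. Section 5.5 already treats off-drug follow-up as workable for its own stops.

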5.4.1.1. Study Treatment Restart or Rechallenge

Study treatment restart or rechallenge after liver chemistry stopping criteria are met by any subject participating in this study is **not allowed**.

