5.5.2. Hematologic abnormalities

The following hematological laboratory abnormalities require withdrawal of study medications *for the remainder of the study* and prompt retesting, ideally within 3-5 days:

- White blood cell count $<2.0 \times 10^9/L$
- Absolute neutrophil count $<1.0 \times 10^9/L$
- Lymphocyte count $<0.5 \times 10^9/L$

Subjects should be followed as appropriate until resolution of the event. Absolute neutrophil count $<1.0 \times 10^9/L$ (Grade 3 or greater) should be reported as an AE.

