12.2. Appendix 2 – Liver Safety Required Actions and Follow up Assessments

Phase II liver chemistry stopping and increased monitoring criteria have been designed to assure subject safety and evaluate liver event etiology (in alignment with the FDA premarketing clinical liver safety guidance).

<http://www.fda.gov/downloads/Drugs/GuidanceComplianceRegulatoryInformation/Guidances/UCM174090.pdf>.

Phase II liver chemistry stopping criteria and required follow up assessments

| Liver Chemistry Stopping Criteria – Liver Stopping Event | |
|--|---|
| ALT-absolute | ALT \geq 5xULN |
| ALT Increase | ALT \geq 3xULN persists for \geq 4 weeks |
| Bilirubin^{1, 2} | ALT \geq 3xULN and bilirubin \geq 2xULN (>35% direct bilirubin) |
| INR² | ALT \geq 3xULN and INR>1.5, if INR measured |
| Cannot Monitor | ALT \geq 3xULN and cannot be monitored weekly for 4 weeks |
| Symptomatic³ | ALT \geq 3xULN associated with symptoms (new or worsening) believed to be related to liver injury or hypersensitivity |

| Required Actions and Follow up Assessments following ANY Liver Stopping Event | |
|--|--|
| Actions | Follow Up Assessments |
| 
 Immediately discontinue study treatment Report the event to GSK within 24 hours Complete the liver event CRF and complete an SAE data collection tool if the event also meets the criteria for an SAE² Perform liver event follow up assessments Monitor the subject until liver chemistries resolve, stabilize, or return to within baseline (see MONITORING below) Do not restart/rechallenge subject with study treatment unless allowed per protocol and GSK Medical Governance approval is granted (refer to Section 5.4.1.1.) If restart/rechallenge not allowed per protocol or not granted, permanently discontinue study | 
 Viral hepatitis serology⁴ Blood sample for pharmacokinetic (PK) analysis, obtained within a week after last dose⁵ Serum creatine phosphokinase (CPK) and lactate dehydrogenase (LDH). Fractionate bilirubin, if total bilirubin\geq2xULN Obtain complete blood count with differential to assess eosinophilia Record the appearance or worsening of clinical symptoms of liver injury, or hypersensitivity, on the AE report form Record use of concomitant medications on the concomitant medications report |

| | |
|--|---|

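### Section 5.4 takes liver stopping cases and persistent or recurrent hematologic cases out of the study, while Appendix 2 and Section 5.5 stop only treatment and let them stay in

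*Protocol*

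**What the plan says.** **Section 5.4 (Withdrawal/Stopping Criteria).** The list opens with "In addition, study medications will be discontinued and the subject withdrawn from the study in the event of any of the following". Two of its items matter here:

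- Liver, sharing a bullet with QTc: "If the liver chemistry stopping criteria (Section 5.4.1) or QTc stopping criteria (Section 5.4.2) are met".
- Hematologic: "Persistent or recurrent hematologic laboratory abnormalities (see Section 5.5.2)".

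**Liver, elsewhere.** Section 5.4.1.1 reads "Study treatment restart or rechallenge after liver chemistry stopping criteria are met by any subject participating in this study is" and ends by stating that it is not allowed. Section 5.4.1 refers sites to Appendix 2 for the required actions. Appendix 2 says "If restart/rechallenge not allowed per protocol or not granted, permanently discontinue study" and, across the page break, "treatment and may continue subject in the study for any protocol specified follow up assessments".

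**Hematologic, elsewhere.** Section 5.5 covers respiratory symptoms and hematologic abnormalities together. After treatment is withdrawn, "where possible subjects should remain in the study (off treatment) in order to complete all remaining visits/assessments". Section 5.5.2 says "The following hematological laboratory abnormalities require withdrawal of study medications" for the remainder of the study, lists three count thresholds, and asks for a prompt retest.

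**The concern.** A site needs to know whether a safety event ends dosing or ends participation. For these two events the protocol gives both answers. Section 7 allows no waivers apart from immediate safety concerns, so a site is not free to choose between them.

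The stake is data after a safety event. A site that follows Section 5.4 may stop the scheduled visits and the daily pain diary. If that happens before Week 6, the primary value can be missing, and Section 9.4.2 then counts the missing pain score as non-response in the responder analyses. Scheduled safety observation also shrinks in the subjects for whom it is most useful.

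**Working it through.** **Step 1. Liver.**

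| Source | Treatment | Study participation |
|---|---|---|
| 5.4 | stopped | withdrawn (mandatory) |
| 5.4.1.1 | no restart for any subject | not addressed |
| Appendix 2, branch for restart not allowed | permanently stopped | may continue |

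Because 5.4.1.1 bars restart without exception, the Appendix 2 branch applies to every liver stopping event. A permission to stay cannot stand beside a mandatory withdrawal, so this conflict is direct.

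**Step 2. Hematologic.**

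| Source | Trigger | Treatment | Study participation |
|---|---|---|---|
| 5.4 | persistent or recurrent abnormality, citing 5.5.2 | stopped | withdrawn |
| 5.5 | any 5.5.2 abnormality | permanently stopped | remain where possible |
| 5.5.2 | a count below threshold | stopped for the rest of the study | not addressed |

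Section 5.5.2 already ends dosing at the first qualifying count. All that the 5.4 item adds is the end of participation, which 5.5 tells sites to avoid where possible. The conflict covers persistent or recurrent cases only.

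**Step 3. The plan's own power.** Inputs from Sections 9.1 and 9.2.1: 20 per arm, SD 3, difference 2.7, two-sided 5%.

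SE = 3 × √(1/20 + 1/20) = 0.949. Noncentrality = 2.7/0.949 = 2.846, with 38 df. Power by the noncentral t is 79.2%, against a stated value of approximately 80%, so the figure reproduces.

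**Step 4. Cost of missing Week 6 values.** The protocol gives no event rate, so one or two affected subjects is an assumption. The MMRM in Section 9.4.1 still uses a subject's earlier visits. As an approximation, take two visits (the last earlier visit and Week 6), known covariance, and correlation r of 0.5 to 0.8 (assumed, not in the protocol). With m of n Week 6 values missing in an arm:

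Var(Week 6 arm mean) = (SD²/n) × [1 + (m/(n − m)) × (1 − r²)]

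Example, m = 1 and r = 0.5: 0.45 × [1 + (1/19) × 0.75] = 0.4678. SE = √(0.45 + 0.4678) = 0.958.

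| Week 6 values missing | r | SE | Power (38 df) | Loss, points |
|---|---|---|---|---|
| none | – | 0.949 | 79.2% | – |
| one | 0.8 | 0.953 | 78.8% | 0.4 |
| one | 0.5 | 0.958 | 78.4% | 0.8 |
| two, same arm | 0.8 | 0.958 | 78.4% | 0.8 |
| two, same arm | 0.5 | 0.968 | 77.6% | 1.6 |

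One missing in each arm differs from two in the same arm by no more than 0.1 point.

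**Step 5. Worst case, subjects deleted (t-test).** 20 against 19: 78.1%, a loss of 1.1 points. 20 against 18: 76.9%, a loss of 2.3. 19 against 19: 77.0%, a loss of 2.2.

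**Step 6. Responder endpoints.** One subject counted as a non-responder is 1/20 = 5 percentage points of an arm.

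**The case against.** **Hematologic: a two-tier reading.** One low count stops drug and prompts a retest; persistence then ends participation. This is coherent, and the words where possible in 5.5 leave some room for it. It is not what the text says, however. Section 5.5.2 defines no persistent or recurrent tier, and 5.5 carves out no exception for one. What stands is that the conflict is narrow: a single low count is not affected.

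**Liver: the Appendix 2 wording is permissive and looks like a general template, whereas 5.4 is specific to this trial.** That may explain how the mismatch arose, but sites are sent to Appendix 2 for required actions and will read both. The algorithm figure in Section 5.4.1 was not in the text reviewed and might show which action was intended, so confidence is a little below high.

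**Withdrawal does not mean all data are lost.** Section 7.1.3 gives early withdrawals the Day 85 procedures and then a follow-up visit. This stands. What is at risk is the remaining scheduled visits and the diary. The detailed 7.1.3 list and the notes to the treatment-period table were not in the text reviewed, so diary handling after withdrawal could not be checked.

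**Events may be rare.** Section 4.7.1 records no reports of neutropenia or leukocyte decreases in the program, and low counts and existing liver disease are excluded at entry. This also stands and keeps the point small.

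**Stronger readings that the protocol does not support.**

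- That respiratory and QTc cases are contradictory too. Persistent respiratory symptoms are not in the 5.4 list, and 5.4.2 agrees with 5.4 that QTc cases leave the study.
- That Section 6.4 contradicts the rest. It says a subject is withdrawn after a code break without saying from what. That is an ambiguity. Making it treatment-only would be a preference, with the cost that some scores would be collected after the investigator knows the arm.
- That the wording biases the comparison. Nothing in the protocol shows these events would differ between arms.

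**Conclusion.** The point holds and is minor. The current text gives opposite instructions on study participation for liver stopping events, and for hematologic abnormalities that persist or recur.

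The loss of power is about 0.4 to 1.6 points under the planned model and at most about 2.3 points if subjects are deleted. Both figures rest on one or two subjects being affected before Week 6, and the first also on a correlation of 0.5 to 0.8. The reason to act is less the power than consistent handling across sites and continued observation after a safety event, at almost no cost.

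**What to change.** In Section 5.4:

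1. Split the shared liver and QTc bullet. Leave QTc in the study-withdrawal list unchanged.
2. Move the liver item and the persistent or recurrent hematologic item out of that list.
3. Reword both as permanent discontinuation of study treatment, with the subject remaining in the study off treatment where possible and completing the remaining visits, the daily pain NRS and safety follow-up.

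This applies to the whole of both items a rule that Section 5.5 and Appendix 2 already contain. It adds no visits beyond the existing schedule. The cost is a wording amendment with the usual ethics committee review under Section 10.2. It does not change the other events in the list, such as serious infection or severe hypersensitivity, which will still end participation and can still cost a Week 6 value.
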